- In the THRIVE group, an estimate of how much time the participant managed to breathe with their mouth closed during the pre-oxygenation period on a 5-point Likert scale: Mouth closed the entire time, mouth open sometimes, mouth open half of the time, mouth open occasionally or mouth open the entire time.

The demographic information and medical history will be collected from the medical chart by one of the study team after the participant has given informed consent to participate in the study. The participant satisfaction data will be collected at the end of the breathing procedures by one of the study team who were conducting the study procedure. This will be done by asking the following questions listed on the Data Collection Sheet:

1. "Please indicate how you felt from a comfort point of view breathing via the nasal oxygen device/Facemask: Completely comfortable, slightly comfortable, neither, slightly uncomfortable, completely uncomfortable."
2. "Please indicate how you felt from an acceptability point of view breathing via the Nasal Oxygen device/Facemask: Acceptable, slightly acceptable, neutral, slightly unacceptable or unacceptable."
3. Which breathing device did you prefer: nasal oxygen device or facemask?

Sample size:

We chose a sample size of 20 participants in each group (40 total participants). No formal statistical sample size analysis was performed. Simulation studies have suggested that using 20 to 40 patients in up-down sequential allocation trials will provide stable estimates of the target interval. In addition, the non-independence and unknown distribution of data of an up-down study prevent the development of theoretically rigorous rules to calculate the necessary sample size[14].

Statistical analysis:

Concentration of EtO₂ will be summarized using means and SD within each group. Data (ordinal) from Likert scales will be described using modes and percentages. Isotonic regression will be used to determine the primary outcome data.

Isotonic regression using the pooled-adjacent-violators algorithm will be used to determine the modified isotonic estimator for the ED90 interval. (Stylianou M et al. Biometrics 2002) In short, the observed success rate (percentage of patients with EtO₂>=90) will be calculated for each time

interval. Isotonic regression using the pooled-adjacent-violators algorithm will then be used to obtain point estimates for the success rates that were constrained to be monotonic increasing with time interval. The modified isotonic estimator for ED_{90} will then be obtained via linear interpolation between the highest time interval with an estimated success rate $<90\%$ and the lowest time interval with an estimated success rate $>90\%$. To provide an interval estimate for EI_{90} and for the probability of success at the sample estimate for the EI_{90} , a 95% confidence interval (CI) will be constructed using the bootstrap approach described by Stylianou et al. To account for the repeated-measures study design, ETO_2 at each time points will be compared across all time points using generalized estimating equations. Using a logit link function, generalized estimating equation analyses were also performed to compare the percentage of patients with effective preoxygenation ($ETO_2 \geq 90$) between different time interval groups.

This protocol has been developed with the assistance of [name] PhD, Biostatistician at the Women's Health Research Institute, BC Women's Hospital. [name] will assist with the statistical analyses of any data collected.

Data management:

De-identified participant data will only be collected by members of the research team using paper data collection forms. Once collated, the data will then be entered onto a password protected Microsoft Excel spreadsheet on a password protected computer in the locked Research Assistant's office. The paper data collection forms will be stored for 5 years following publication of the study and then destroyed using the hospital's privacy and confidentiality shredding service. Participant identifiable data will not be recorded.

Our project will be registered with the Research and Development department at the BC Women's Hospital. This study will also be registered online with <http://www.clinicaltrials.gov/>.

We will write up the results of the study and submit for presentation at medical conferences and publication in a medical journal so that we can tell other doctors about our findings. This may help to improve care for patients at other hospitals.

Safety:

No harm is expected from participating in this study. However, we are aware that this study aims to collect data during a potentially stressful admission to hospital. Therefore, data collection will always be secondary to the delivery of standard patient care and maternal wellbeing.

It is well described that prolonged high levels of oxygen (hyperoxia) can cause tiny parts of the lung to collapse and lead to the production of oxygen free radicals, which may cause lung inflammation[15]. However, shorter periods of hyperoxia have not been shown to cause any adverse inflammatory effects when breathing 100% oxygen for 3.5 hours[16]. In addition, increased levels of oxygen free radicals have been shown to be independent of the inspired concentration of oxygen during Cesarean delivery and this is not known to affect fetal outcomes[17][18] . During this study, participants will only be breathing 100% oxygen for a maximum of 8 minutes and therefore this should not cause any adverse effects to either the participants or their baby.

Feasibility:

At BCWH we perform 15-20 elective Cesarean deliveries under neuraxial anesthesia per week. A conservative recruitment of approximately 10% of these patients would equate to an average of 2 participants per week. We anticipate that this study would be completed in approximately 20 weeks from the start of recruitment.

Financial cost:

The current cost of a disposable anesthetic facemask, heat moisture exchange filter, mouthpiece and nose clip at BCWH are \$3.01, \$2.71, \$0.74 and \$0.98 respectively. The Optiflow™ THRIVE system has previously been purchased by the Department of Anesthesia at BCWH. The disposable components for the Optiflow™ THRIVE system are the nasal cannulae (including filter) and multi-patient circuits (which can be used for 24hrs), costing \$24 and \$65 respectively. This equates to a maximum total cost of approximately \$7,715 for the study, but could be less if multiple patients use a single THRIVE circuit within 24hrs. We will apply for research grant funding; however, if this is not successful, it will be funded by the Department of Anesthesia at BCWH.

Disclosure:

Nothing to declare.

References:

1. Girard T, P.A., *The obstetric difficult airway: if we can't predict it, can we prevent it?* . Anaesthesia, 2017. **72**: p. 143-7.
2. Porter, R., I.J. Wrench, and R. Freeman, *Preoxygenation for general anaesthesia in pregnancy: is it adequate?* Int J Obstet Anesth, 2011. **20**(4): p. 363-5.

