High flow nasal pre-oxygenation could offer significant clinical benefits in obstetric anesthesia[10]. It can be prepared ahead of time for immediate use during an emergency Cesarean delivery. During THRIVE pre-oxygenation, the anesthesiologist can prepare drugs, equipment or attempt neuraxial anesthesia

instead of holding a mask. It can also continue during airway manipulation, permitting apneic oxygenation, which may transform managing the difficult obstetric airway from a time-pressed, anxious situation to one where there is time to carefully make considered decisions[11].

Recently, our department conducted a study (REB (#H17-01996) Pre-Oxygenation in Pregnancy (POP study), ClinicalTrials.gov identifier: NCT03310723) comparing THRIVE pre-oxygenation to conventional facemask for healthy, term parturients [12]. Pre-oxygenation using THRIVE was non-inferior to conventional tight-fitting facemask following 3 minutes of tidal volume breathing and was well tolerated[12]. However, this study did not examine which technique could provide more rapid pre-oxygenation. Knowledge of this information would be immensely helpful and could help anesthesiologists decide the best technique for rapid pre-oxygenation. For example, in situations such as in emergency Cesarean deliveries where the baby needs imminent delivery and there is limited time for optimal pre-oxygenation, the best technique is unknown. Furthermore, the maximum rate of oxygenation using THRIVE has not been measured in any patient group.

The purpose of this study is to identify the effective time interval using THRIVE to achieve an end tidal oxygen (EtO_2) $\geq 90\%$ in 90% of healthy parturients (i.e. effective time interval (EI90)) using a biased-coin design. We also seek to directly compare EI90 of THRIVE to EI90 of facemask using the same protocol.

Study design and methodology

This will be a prospective, randomized, sequential allocation study with a biased-coin design. The purpose of this study is to identify the EI90 using THRIVE versus conventional facemask to pre-oxygenate 90% of healthy parturients to an $\text{EtO}_2 \geq 90\%$.

Hypothesis:

We hypothesize that in healthy parturients undergoing tidal volume breathing, the EI90 for THRIVE pre-oxygenation will be shorter than the EI90 for facemask pre-oxygenation.

Primary objective:

1. To determine the EI₉₀ for THRIVE and facemask pre-oxygenation using tidal volume breathing.

Primary outcome:

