1. Duration to achieve $\text{EtO}_2 \geq 90\%$ after tidal volume breathing using THRIVE and facemask pre-oxygenation.

Sequential allocation method with a biased-coin design:

1. Positive response is defined as an EtO_2 concentration $\geq 90\%$
2. Negative response is defined as an EtO_2 concentration $< 90\%$
3. Increment:
 - a. THRIVE pre-oxygenation – first participant starts at 3 minutes, increments of 1 minute (except lowest interval of 30 seconds), maximum 8 minutes, minimum 30 seconds. Possible time intervals 30s-1-2-3-4-5-6-7-8 minutes.
 - b. Facemask - first participant starts at 3 minutes, increments of 1 minute (except lowest interval of 30 seconds), maximum 8 minutes, minimum 30 seconds. Possible time intervals 30s-1-2-3-4-5-6-7-8 minutes.

4. Allocation:

- a. The time interval for pre-oxygenation for subsequent study participants is based on the whether the previous participant achieves a negative or positive response (as defined above).
- b. The time for pre-oxygenation for subsequent participants will be adjusted using a biased coin up-down sequential allocation method described by Durham and Flournoy with the aim of estimating the EI90[13]. When EI90 is to be determined ($\tau = 0.9$), the probability (B) = $(1 - \tau)/\tau = (1 - 0.9)/0.9 = 0.1/0.9 \approx 0.11$.
- c. If a negative response is achieved (EtO₂ concentration <90%), when the next participant uses the same pre-oxygenation method, they will receive the next upper time interval for that pre-oxygenation method. For example, if the first participant achieves an EtO₂ concentration <90% using THRIVE for 3 minutes, the next participant who uses THRIVE pre-oxygenation will do so for 4 minutes.
- d. If a positive response is achieved (EtO₂ concentration $\geq 90\%$), when the next participant uses the same pre-oxygenation method, they will receive with probability B ≈ 0.11 the next lower time interval and with probability 1 – B = 0.89, the same time interval as the previous participant. For example, if the first participant achieves an EtO₂ concentration $\geq 90\%$ using THRIVE for 3 minutes, the next participant who uses THRIVE pre-oxygenation will stay at the same level breathing for 3 minutes.

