Participants will be randomly assigned to one of 2 groups: THRIVE or facemask (control). Participants in the THRIVE group will first receive pre-oxygenation using the Optiflow™ THRIVE nasal high-flow cannula system (Fisher and Paykel Healthcare Ltd, Auckland, New Zealand) followed by pre-oxygenation via a conventional anesthetic facemask, as is performed in routine clinical practice. Participants in the facemask (control) group will first receive pre-oxygenation via a conventional anesthetic facemask followed by pre-oxygenation using the Optiflow™ THRIVE nasal high-flow cannula system. It is anticipated that participation in this study will take approximately 30 mins (15 mins for informed consent and 15 minutes to complete the study protocol).

Baseline recording

Each participant will be taken to the operating room, usually where their elective Cesarean delivery will take place if applicable. The participant will be placed on the operating table, lying down in a ramped position using the Troop™ (Goal Medical, LLC, Eugene, OR, USA) elevation pillow (Figure 1) and with a right lateral pelvic wedge to minimize aortocaval compression. This is the same position used during an elective Cesarean delivery. Before assessing the different pre-oxygenation techniques, each participant will be asked to breathe 21% oxygen (room air) at a rate of $12 \text{ L} \cdot \text{min}^{-1}$, in a normal way for 30s, via a mouthpiece with a clip on their nose. This will allow time for the participant to get used to the nose clip and to both practice making a tight seal around and breathing through the mouthpiece. The mouthpiece will be connected to an anesthetic circle system with a 2L reservoir bag, heat moisture exchange filter and an oxygen analyzer. Baseline values will be recorded for EtO_2 concentration, oxygen saturation, respiratory rate, and heart rate after the 30s have been completed. In order to record an accurate EtO_2 concentration using THRIVE, we plan to quickly remove the THRIVE system and change to a mouthpiece and nose clip attached to an anesthetic breathing circuit, as used in our previous study[12].

In the THRIVE group, after the initial baseline recordings, the following 2 stages will take place.

Stage 1: THRIVE pre-oxygenation

1. The THRIVE system will be applied, with 100% oxygen at an oxygen flow rate of $50 \text{ L} \cdot \text{min}^{-1}$.

2. An AirLife™ Adult Oxygen Mask will then be applied overtop of the THRIVE system (Figure 2).

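### The EI90 interpolation rule uses strict inequalities, so it passes over an interval estimated at exactly 90%; a rule for one-sided data is also unwritten

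*Combined protocol and SAP*

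**What the plan says.** The primary analysis is in the Statistical analysis section of the combined protocol and SAP. Success rates per time interval are smoothed with the pooled-adjacent-violators algorithm (PAVA). The EI90 "will then be obtained via linear interpolation between the highest time interval with an estimated success rate" strictly below 90% "and the lowest time interval with an estimated success rate" strictly above 90%. The 95% confidence interval "will be constructed using the bootstrap approach described by" a cited method paper, with no further detail. The description of the estimator is openly abridged: it opens "In short, the observed success rate".

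The target is defined at the end of the Background as the interval that reaches the end-tidal oxygen threshold "in 90% of healthy parturients (i.e. effective time interval (EI90)) using a biased-coin design".

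The design features that bear on the point are:

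- **Start and grid** (Sequential allocation, item 3): "first participant starts at 3 minutes, increments of 1 minute (except lowest interval of 30 seconds"), for both methods, up to 8 min.
- **Step-down** (Sequential allocation, item 4): after a success the next participant on that method moves down with probability about 0.11.
- **Sample size:** "We chose a sample size of 20 participants in each group (40 total participants").
- **Both methods per participant** (Interventions): the THRIVE group has THRIVE "followed by pre-oxygenation via a conventional anesthetic facemask, as is performed in routine clinical practice", and the control group has the reverse order. A method could therefore contribute 20 responses, or 40 if both stages count.

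**The concern.** An estimate of exactly 90% is attainable with these sample sizes (9/10, 18/20, or a pooled block). When it occurs, the data put one interval exactly on the target, yet the written rule interpolates across that interval or returns nothing. The reported EI90 then disagrees with the plan's own definition of it.

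The same sentence is silent when every tested interval is estimated above 90%, or every one below. The rule then produces no number for the primary outcome, and someone must decide what to report after seeing the results of an unblinded trial. Bootstrap resamples can fall into the same state even when the observed data have a bracket. How they are handled can then move a confidence limit.

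**Working it through.** **The plan's own figure.** B = (1 - 0.9)/0.9 = 0.111 and 1 - B = 0.889, which match the stated 0.11 and 0.89. The sample size has no formula to reproduce.

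**Ties, by hand.** Interpolated EI90 = t1 + (0.9 - p1)/(p2 - p1) x (t2 - t1), where 1 and 2 are the lower and upper bracket points. The counts are illustrative.

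| Successes/tested | Rule as written | Exactly 90% accepted |
|---|---|---|
| 2/4, 9/10, 6/6 at 2, 3, 4 min | 2 + (0.9 - 0.5)/(1 - 0.5) x 2 = 3.6 | 3.0 |
| 8/9, 9/10, 1/1 at 2, 3, 4 min | 2 + (0.9 - 8/9)/(1 - 8/9) x 2 = 2.2 | 3.0 |
| 9/10, 10/10 at 3, 4 min | no interval below 90%: no value | 3.0 |
| 3/4, 9/10 at 3, 4 min | no interval above 90%: no value | 4.0 |

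The shift can go either way.

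**How often, under assumed curves.** The documents give no response curve, so one is assumed: P(success at t) = 1/(1 + (1/9)(EI90/t)^slope), which equals 0.9 at t = EI90, with slopes 2, 3 and 5. Each sequence starts at 3 min on the grid 0.5, 1, 2, ..., 8 min with B = 1/9, and PAVA is computed in exact fractions.

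- Exact ties, true EI90 of 2-6 min: about 3-7% of sequences. The mean absolute shift is about 0.4-0.8 min where the written rule returns a value.
- No value under the written rule:

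| True EI90 | 20 responses | 40 responses |
|---|---|---|
| 2 min | 25-28% | 8-11% |
| 3 min | 9-14% | 3-5% |
| 4-6 min | 2-8% | 0.2-7% |

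Accepting exactly 90% still leaves about 23-26% without a value at 2 min with 20 responses, because most of these sequences have every estimate above 90%. The one-sided case therefore needs its own sentence.

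**Bootstrap, illustrative only.** This assumes binomial resampling at the isotonic rates with the observed counts, which the plan does not state. Take 2/3, 12/13, 4/4 at 2, 3, 4 min.

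- EI90 = 2 + (0.9 - 2/3)/(12/13 - 2/3) = 2.91 min.
- A resample has no interval below 90% if it gives 3/3 at 2 min and at least 12/13 at 3 min (pooled, 15/16 = 0.94). The probability is (2/3)^3 x [(12/13)^13 + (12/13)^12] = 0.2963 x 0.7360 = 21.8%.
- Full enumeration, with exactly 90% accepted, gives a 95% CI of 2.70-3.57 if these resamples are dropped, 2.00-3.57 if set to the lowest interval tested, and open below with upper limit 3.57 if ranked lowest. Only the lower limit changes.

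**The case against.** The strongest reply is that the paragraph is a summary. It names the estimator, cites the paper behind it and takes the bootstrap wholly by reference, so conventions for ties and one-sided data may already be fixed there. That stands for the one-sided and bootstrap parts: the documents show only that the protocol text does not repeat any such convention. It has less force for the tie, because the text does state an inequality, and a programmer who follows it gets 3.6 instead of 3.0 min.

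A second reply is that the strict sign is loose wording and that a sensible analyst would report the interval at 90%. That is plausible, and ties are uncommon. Nor does accepting exactly 90% always land closer to the truth. It did in most simulated scenarios, but at a true EI90 of 6 min, slope 2 and 20 responses, the mean absolute error among ties was 1.43 min against 1.20 as written. The answer is not always unique either: with 40 responses, 11-26% of ties in most scenarios were pooled blocks spanning two or more intervals.

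Third, one-sided data are mainly a limit of information. No wording recovers a point estimate from them, and a bound can be thin: 1/1 at 2 min and 19/19 at 3 min would be reported as below 2 min on one response. This stands, and it is why the number of responses should accompany any bound.

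A reader might infer that the primary outcome will often be inestimable, or that the planned confidence interval is invalid. The documents support neither. The 25-28% needs a true EI90 of 2 min with only 20 responses, and nothing in the plan favours that value. The bootstrap percentages describe an assumed resampling scheme, and the plan attaches no test or decision to the lower limit.

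**Conclusion.** The point holds for the rule as written. An interval estimated at exactly 90% is skipped, contrary to the plan's definition of EI90; this follows from the wording and needs no simulation. Its expected effect is modest: about 3-7% of sequences under the assumed log-logistic curves, with a mean shift of 0.4-0.8 min. It is worth correcting because it concerns the primary estimate for both methods and costs almost nothing.

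The missing convention for one-sided data and for bootstrap resamples is a minor clarification. Its frequency depends on true curves that the documents do not give, and the cited paper may already cover it.

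**What to change.** 1. **Tie.** Define the upper bracket as the lowest tested interval whose isotonic estimate is at least 90%. State that if this estimate is exactly 90%, that interval is the EI90, including when it is the lowest interval tested, where there is no lower bracket to interpolate from. If a pooled block lies at exactly 90%, its lowest interval is taken by convention.
2. **One-sided data.** State in advance that EI90 is reported as below the lowest interval tested (all estimates above 90%) or above the longest interval tested (none reaching 90%), with the number of responses at that interval.
3. **Bootstrap.** State the resampling scheme, and that resamples without a bracket are counted and reported, not silently dropped. Ranking them beyond the numeric values and reporting an affected limit as open-ended is one workable choice among several.
4. **Cited paper.** If it sets other conventions for items 2 and 3, write those into the SAP instead.

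The cost is one changed inequality, a few sentences and small code changes; trial conduct and sample size are untouched. The tie fix has a negligible downside. Under item 2, some results will be bounds and not point estimates.

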3. The duration of this pre-oxygenation will again be 3 minutes for the 1st participant. Based on the sequential allocation biased coin method, we intend to use 1 minute increments, either increasing or decreasing the duration of pre-oxygenation based on the response of the previous participant.
4. Once the pre-oxygenation is completed, the participant will be asked to take and hold a deep breath for up to 5s. The facemask will be quickly removed, a nose clip will be placed on the

participant's nose and the participant will be given the mouthpiece to insert into their mouth and asked to make a tight seal around it.

5. The participant will then be asked to exhale fully into the mouthpiece for the EtO₂ concentration to be analyzed and recorded (primary endpoint).
6. Oxygen saturation, respiratory rate and heart rate will be recorded at the start of the second pre-oxygenation period and every 60s until completed.

In the facemask (control) group, after the initial baseline data recordings, the following 2 stages will take place:

Stage 1: Facemask (control) pre-oxygenation

1. Participants will be assigned to receive pre-oxygenation via a conventional facemask held by the study anesthesiologist, set at 100% oxygen and a rate of 15 L.min⁻¹.
2. The duration of this pre-oxygenation will be 3 minutes for the 1st participant. Based on the sequential allocation biased coin method, we intend to use 1 minute increments, either increasing or decreasing the duration of pre-oxygenation based on the response of the previous participant.
3. Once the pre-oxygenation is completed, the participant will be asked to take and hold a deep breath for up to 5s. The facemask will be quickly removed, a nose clip will be placed on the participant's nose and the participant will be given the mouthpiece to insert into their mouth and asked to make a tight seal around it.
4. The participant will then be asked to exhale fully into the mouthpiece for the EtO₂ concentration to be analyzed and recorded (primary endpoint).
5. Oxygen saturation, respiratory rate and heart rate will be recorded at the start of the second pre-oxygenation period and every 60s until completed.

Stage 2: THRIVE pre-oxygenation

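### The bootstrap interval for EI90 is labelled 95% but probably covers clearly less than that at 20 to 40 results per method, and the interpolation has no value when no tested interval falls below 90%

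*Combined protocol and SAP*

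**What the plan says.** The Statistical analysis section fits isotonic regression (pooled adjacent violators) to the success rates by time interval. The EI90 "will then be obtained via linear interpolation between the highest time interval with an estimated success rate" under 90% and the lowest one above it. For precision, "a 95% confidence interval (CI) will be constructed using the bootstrap approach" of a cited methods paper. The text does not give the resampling scheme, the type of bootstrap interval, how untested levels are filled, or what happens when the fitted curve does not cross 90%.

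The Sample size section says "We chose a sample size of 20 participants in each group (40 total participants" in all) and "No formal statistical sample size analysis was performed". Its support is that 20 to 40 patients "will provide stable estimates of the target interval". That speaks to the point estimate; coverage of the interval is not mentioned.

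The sequential allocation section fixes the grid ("Possible time intervals 30s-1-2-3-4-5-6-7-8 minutes"), a start at 3 minutes, one level up after every failure, and one level down after a success with probability of about 0.11.

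**The concern.** The EI90 is the primary objective, and this interval is its only planned statement of precision. A 90th percentile is being estimated from very few failures, on a coarse grid, by a walk that starts at 3 min wherever the truth lies. Bootstrap intervals need not reach their nominal level in that setting, and nothing in the plan checks whether they do.

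The hypothesis is that THRIVE has the shorter EI90, yet the Statistical analysis section gives no rule for comparing the two EI90 values. Readers are therefore likely to compare the two intervals by eye, and an interval with less than its stated coverage would overstate how precisely each EI90 is known.

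**Working it through.** **Inputs from the documents.** Grid 0.5, 1, 2, ..., 8 min; start 3 min; B = (1 - 0.9)/0.9 = 0.111, which reproduces the plan's figure. There are 20 results per method if only the randomized first stage counts. There are up to 40 if both stages count: each participant uses both methods, and the second stage follows the same rule ("The duration of this pre-oxygenation will again be 3 minutes for the 1st participant"). The sample size has no formula to reproduce.

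**Assumed.** The true success curve, which the documents do not give, and the bootstrap variant.

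**1. How few failures there are.** Once the walk has settled, upward and downward moves balance: P(failure) = B × P(success). So P(failure) = 0.111/1.111 = 0.10, or about 2 failures in 20 results and 4 in 40. Simulated averages, which include the early walk, were 1.0-4.1 and 3.0-6.2.

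**2. How slowly the walk descends.** A step down needs on average 1/0.111 = 9 successes. Going from 3 to 2 to 1 min takes about 18 successes, nearly all of a 20-result sequence.

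**3. One curve in detail.** Lognormal response times, EI90 3.5 min, log-SD 0.5; 1,500 trials with 400 resamples each. Four resampling schemes: re-running the walk from the fitted curve with flat tails or with 0/1 tails, binomial redraw with level counts fixed, and case resampling.

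| Nominal 95% interval | Coverage, 20 results | Coverage, 40 results |
|---|---|---|
| Percentile and bias-corrected, four schemes | 74-84% | 79-90% |
| Basic | 46-54% | 59-61% |
| Percentile, undefined resamples sent to open ends | 78-93% | 82-93% |

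- *Width.* The estimator's own 2.5-97.5% range was 2.70 to 5.30 min at 20 results (5.30 - 2.70 = 2.6 min) and 2.83 to 5.20 at 40 (2.4 min). Mean percentile interval widths were only 1.3-1.9 and 1.5-1.8 min.
- *Bias.* The mean estimate was about 0.2 min above 3.5.
- *Grid.* True success on this curve is 83.5% at 3 min and 93.9% at 4 min. A straight line reaches 90% at 3 + (90 - 83.5)/(93.9 - 83.5) = 3.62 min, so interpolation alone accounts for part of that shift.

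**4. Over many curves.** Mean coverage:

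| Set | 20 results | 40 results |
|---|---|---|
| 9 curves, EI90 2.5-5.5 min: walk re-run, percentile (two tail rules) | 71%, 76% | 79%, 82% |
| Same: case resampling, percentile | 75% | 87% |
| Same: case resampling, open-ended (best of 16 variants) | 86% | 92% |
| Same: basic | 45-54% | not summarised |
| 18 lognormal curves, EI90 1.5-6 min, log-SD 0.15-0.5: 10 variants | 58-71% | 78-88% |
| 21 lognormal curves: 6 variants | 53-78% | 75-90% |

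No variant reached 95% on average in any set. Monte Carlo error is about 2 points per cell with 400 trials (√(0.75 × 0.25/400) = 0.022), about 3 with 200, and about 1 for the 1,500-trial curve.

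**5. Spread between curves.** At EI90 6 min, log-SD 0.5, the walk re-run percentile interval (flat tails) covered 43% at 20 results and 75% at 40. At EI90 3 min, log-SD 0.15, it covered 95% and 94%, and case resampling covered 94% and 98%.

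**6. When the interpolation fails.** No tested interval had estimated success below 90% in about 0-40% of trials at 20 results and 0-12% at 40, depending on the curve. For EI90 2.5 min, log-SD 0.4, the estimate was undefined in 17% and 5%.

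**The case against.** **The algorithm is in a paper that is not available here.** This is fair. The variant matters: on the 1,500-trial curve at 40 results, basic intervals covered 59-61% and open-ended ones 82-93%. Nobody can say from the documents exactly how the planned interval performs. What stands is that every variant tried fell below 95% on average.

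**A reader might infer that the interval under-covers whatever the truth.** The material does not support that. With a steep curve and EI90 on or near a grid time of 2 or 3 min, some variants reach 93-98%, and the best variant averages 92% at 40 results in the nine-curve set. Every figure is conditional on an assumed curve.

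**The 20-result figures may not apply.** If both stages enter the analysis, as the stage-by-stage procedures suggest, there are 40 results per method and the milder figures are the relevant ones. They are still short of 95%.

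**A reader might infer that the two intervals will show a false difference between THRIVE and facemask.** The plan states no rule based on their separation, and no false-difference rate was computed. This is a risk of misreading, not an established error in the plan.

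**A reader might infer that a parametric interval should replace the bootstrap.** A two-parameter logistic in log time with weak priors covered 93-100% against lognormal truth, which is close to its own shape. With success levelling off at 92% it covered 86% at 20 results and 77% at 40; with a slow 12% subgroup, 75% and 82%. It is a useful second view, not a clear replacement.

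**Conclusion.** The concern holds in a conditional form. Under most of the curves assumed, an interval of this kind covers on average roughly 55-80% at 20 results and 75-90% at 40. Against the 5% implied by the label, it would then miss the true EI90 in 20-45% of trials (four to nine times as often) or 10-25% (two to five times). Basic intervals did worse than this and the best open-ended variant did better.

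Narrowness is only part of the cause. Few failures, upward bias, interpolation across a coarse grid and, at 20 results, a walk that may not have moved far from 3 min all contribute. The result rests on assumed success curves and on stand-ins for the cited bootstrap.

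The missing rule for a curve that does not fall below 90% rests on less: the stated interpolation plainly has no lower point in that case. Only its frequency depends on assumptions.

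**What to change.** Keep the isotonic estimate and the bootstrap, and add to the Statistical analysis section:

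1. Simulate the interval's coverage at the achieved number of results per method, over a stated range of success curves, with the bootstrap algorithm written out. Report that coverage beside the interval. Do not present the interval as 95% without this qualification, and do not use separation of the two intervals as evidence that the methods differ.
2. When no tested interval has estimated success below 90%, report EI90 as at or below the lowest tested interval, with a one-sided limit. When none is above 90%, report it as above the highest tested interval, again with a one-sided limit.
3. As a sensitivity analysis, add an interval from a two-parameter monotone model in log time fitted to all responses for that method, and state its parametric assumption.

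The cost is some SAP wording, a short simulation program and a less favourable precision statement. In the lognormal scenarios at 40 results the model-based interval had a median width of about 0.9-5.1 min, against mean bootstrap widths of about 0.4-2.1 min.
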